4.1 Hypothesis

Our central hypothesis is that nipple stimulation with an electronic breast pump to induce labor increases spontaneous vaginal delivery, shortens duration of labor induction, improves patient-reported pain scores during labor, improves patient satisfaction and sense of self agency with the birthing process, and improve scores on the postpartum depression scale. We also hypothesize that participants assigned to nipple stimulation therapy during labor will be more likely to use breastfeeding as the sole source of nutrition at hospital discharge, which will be associated with improved maternal perception of milk supply, less severe newborn weight loss, and sustained breastfeeding for the recommended 6 months. Secondly, we hypothesize that intrapartum nipple stimulation will not increase fetal or neonatal morbidity outcomes. Last, by examining cost of care and health-related quality of life, we hypothesize that performing nipple stimulation therapy during labor will be more cost-effective than the comparator after considering their overall impact on labor and delivery, breastfeeding, and early infant nutrition and care in the first 6 months.

We also hypothesize that nipple stimulation therapy invokes the wide cascade of events that promote labor to a greater extent than IV oxytocin alone. We hypothesize that oxytocin in the plasma of patients performing nipple stimulation will rise less than among subjects receiving IV oxytocin at the time when the subject is first contracting regularly. We hypothesize that other proteins associated with labor (including but not limited to IL6, IL1beta, plasminogen activator inhibitor 1, C reactive protein, ICOS ligand, and ERP29 will rise more in the circulation of subjects receiving nipple stimulation therapy compared with IV oxytocin. We hypothesize that urinary metabolites of prostaglandin E2 and F2alpha will be higher in subjects receiving nipple stimulation therapy. We hypothesize that, on a systematic level, plasma changes among subjects partaking in nipple stimulation will differ from subjects receiving IV oxytocin. We hypothesize that nipple stimulation therapy will have earlier secretory activation as measured by milk sodium and conductivity) in the early days postpartum, compared to individuals receiving IV oxytocin alone.

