6.1.2 Method of Assignment/Randomization

Enrolled subjects will be randomly assigned in a 1:1 ratio to both study groups. A web-based randomization sequence will be prepared using blocks of variable sizes, stratified by study site and amniotic membrane status (intact versus ruptured), and maintained centrally by the study statistician. The advantage of this method is that it provides a good probability of balance, and future assignments are unpredictable. A subject's group assignment will be obtained only after the subject is confirmed to continue to meet inclusion criteria, and a study number is entered and locked in using *REDCap* (Research Electronic Data Capture), an established, secure, web-based capture and management tool developed at Vanderbilt University. Although blinding of both subjects and their obstetrical clinicians would be ideal, blinding is clearly not possible in this trial. We will minimize systematic bias by applying the

same standard procedures for other labor and management strategies between groups at each study site. Further, the group assignment of subject will not be taken into account by trained study staff collecting maternal and neonatal outcomes. Importantly, the main study outcomes of spontaneous vaginal delivery and breastfeeding as the sole source of infant nutrition at hospital discharge are objective measures.

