6.3.1 Study Schedule

There will be five expected study visits or encounters:

Study Encounter #1	
 • Screening and consent • Enrollment and randomization • Assess subject's baseline pain level using visual analog scale • Administer Edinburgh Postnatal Depression Scale to establish baseline • Administer Infant Feeding Intention Survey to establish baseline • Administer EQ-5D questionnaire to establish baseline • Initiation of assigned intervention • Assess subject's pain level two hours after intervention start using visual analog scale • Plasma and urine samples will be collected at Yale site • Milk samples will be collected 	During hospitalization for induction of labor
Study Encounter #2	
 • Assess subject's pain experienced during childbirth with visual analog scale • Administer Labour Agency questionnaire • Administer Birth Satisfaction Scale-Revised questionnaire • Administer EQ-5D[™] questionnaire • Administer EQ-TIPS[™] questionnaire • Milk samples will be collected up to twice a day (if applicable) postpartum 	During hospital postpartum stay prior to discharge
Study Encounter #3	
 • Administer PIMS questionnaire • Administer EQ-5D[™] questionnaire • Administer EQ-TIPS[™] questionnaire 	Contacted by email or text message 2 weeks postpartum

Study Encounter #4	
 • Administer Maternal Breastfeeding Evaluation Scale (MBES) questionnaire to all subjects who report at least one attempt at breastfeeding during the postpartum period. • Administer Edinburgh Postnatal Depression Scale questionnaire • Administer EQ-5D[™] questionnaire • Administer EQ-TIPS[™] questionnaire 	Contacted by email or text message 4-12 weeks postpartum
Study Encounter #5	
 • Administer short questionnaire to assess infant feeding method • Administer EQ-5D[™] questionnaire • Administer EQ-TIPS[™] questionnaire 	Contacted by email or text message 6 months postpartum

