6.4.2 Sample Size Considerations

1) Total sample size for the trial: The sample size for the trial is based on the primary outcome of spontaneous vaginal delivery. Therefore, the sample size of n=988 is selected for this proposed study to detect a 10% absolute increase while accounting for an expected 5% attrition rate. We then estimate, on the basis of the sample size for the primary outcome, the power we will have to detect clinically significant differences in the secondary outcomes.

Sample size estimation for primary outcome:

Detectable absolute difference	Anticipated with nipple stimulation therapy	Total Sample size Across 2 Study Groups for 90% power
15%	79%	426
14%	78%	492
13%	77%	574
12%	76%	676
11%	75%	812
10%	74%	988
9%	73%	1,222

All sample size and power estimates are based on two-tailed tests. *This is important because we will be powered to detect both increases and decreases in outcomes with intrapartum nipple stimulation therapy (intervention) versus immediate synthetic oxytocin infusion without nipple stimulation (comparator).* The expected rate of spontaneous vaginal delivery in the setting of immediate synthetic oxytocin infusion without nipple stimulation used for the sample size estimation is based on averaged institutional data from the study sites. We estimate that a total of **988** (494 nipple stimulation therapy and 494 immediate synthetic oxytocin infusion without nipple stimulation) will be sufficient to detect a **10% absolute difference** (estimated 74% versus 64%) in spontaneous vaginal delivery with 90% power (alpha of 0.05).

Justification: At first glance, the anticipated 10% or greater absolute increase in the spontaneous vaginal delivery rate in our proposed trial appears modest. On the contrary, because the potential public health impact is large, this effect size is significant. It is estimated that 40% of the *one million* women who undergo inpatient labor induction each year in the U.S. are nulliparas. Therefore, a 10% increase in spontaneous vaginal delivery translates to 40,000 more spontaneous vaginal deliveries and *40,000 fewer operative deliveries each year*. Avoiding 40,000 operative deliveries each year will have substantial impact on overall morbidity and healthcare resource utilization in the U.S. and beyond.

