6.4.3 Planned Analyses

6.4.3.1 Primary Analyses

1) Overview: Data analyses will adhere closely to the CONSORT guidelines. Analyses will follow the intention-to-treat principle in which subjects will be analyzed in the group to which they were randomized, regardless of whether or not they received the assigned intervention.

2) Primary Analyses:

Descriptive statistics will characterize the group of individuals recruited and investigate comparability of the two study groups at baseline. Formal statistical testing will be limited to select baseline characteristics considered to be prognostic factors for the primary outcome including hospital admission body mass index (BMI), primary indication for labor induction, Bishop score at randomization, and birth weight. Categorical variables will be compared between trial groups by using the Chi-squared or Fisher's exact tests as appropriate, and continuous variables will be compared using Student's t-test or Wilcoxon Rank Sum Test, as appropriate. Distributions of continuous variables will be assessed by visual inspection of histograms.

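### A pre-intervention pain score is collected from every woman, but no analysis in the protocol commits to using it when 2-hour labor pain is compared between arms

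*Protocol*

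**What the plan says.** **The outcome.** Section 4.1 includes in the central hypothesis that nipple stimulation "improves patient-reported pain scores during labor". Section 5.2.2 makes this a secondary outcome: VAS pain 2 hours after the intervention starts.

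**The baseline score.** The first study encounter in Section 6.3.1 includes "Assess subject's baseline pain level using visual analog scale". Section 6.2 places this reading before the intervention and gives obtaining a baseline as its purpose. Section 6.3 (Subject Management and Follow-Up) asks it of all subjects, after randomization.

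**The analysis.**
- Section 6.4.3.1 has a paragraph on the comparability of the groups at baseline. It ends with "continuous variables will be compared using Student's t-test or Wilcoxon Rank Sum Test, as appropriate" and "Distributions of continuous variables will be assessed by visual inspection of histograms". Section 6.4.3.4 gives a similar rule for subject characteristics.
- The next paragraph of 6.4.3.1 gives outcome tests: chi-square or Fisher for categorical outcomes, log-rank and Cox for labor length, and Wilcoxon for newborn weight loss and the PIMS and MBFES scores. Pain is not mentioned.
- Sections 6.4.3.2 and 6.4.4 allow covariate-adjusted analyses where needed, partly to sharpen the treatment comparison. Quantile regression is a possibility for continuous secondary outcomes. All of this is labelled exploratory, and baseline VAS is not named.
- The biospecimen plan in 6.4.3.2 uses ANCOVA on the baseline biomarker level as a supportive analysis.

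**The concern.** A pre-treatment reading on the same scale is usually a good predictor of the later reading. Eligibility (Section 5.3.2) admits women with intact membranes and a cervix under 6 cm, and women with ruptured membranes and fewer than 3 contractions per 10 minutes. Pain at entry can be expected to vary. If that variation stays in the error term, the interval for the arm difference is wider than it need be, and any chance imbalance in entry pain passes into the estimate.

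If the generic rule is taken to cover pain, there is a second cost. Whether a difference in means or in ranks is tested would be settled only after the histograms are seen. For weight loss, PIMS and MBFES the protocol settles it in advance.

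At stake is the precision of one secondary outcome. Randomization keeps the unadjusted comparison valid.

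**Working it through.** **1. Number per arm, checked against the protocol's own figure.** The inputs from Section 6.4.2 are 64% versus 74%, 90% power, alpha 0.05 ("All sample size and power estimates are based on two-tailed tests"), and a sample chosen "to detect a 10% absolute increase while accounting for an expected 5% attrition rate". Allocation is 1:1 (6.1.2).

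- The two-proportion formula without continuity correction gives 448 per arm; with it, 468.
- Allowing for attrition, 468 / 0.95 = 492.6, so 493 per arm and 986 in total, against 988 stated. The other six rows of the table reproduce exactly by the same route.
- Evaluable per arm: 494 × 0.95 = 469.3, taken as 469. This assumes that the 5% attrition also describes missing 2-hour VAS scores.

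The protocol gives no SD, target difference, power or baseline correlation for the VAS, so there is no pain figure to reproduce. Everything below is conditional.

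**2. Variance.** Let r be the correlation between baseline and 2-hour VAS (assumed). Regression on baseline multiplies the residual variance by 1 − r².

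- r = 0.3: 1 − 0.09 = 0.91, a fall of 9%
- r = 0.5: 1 − 0.25 = 0.75, a fall of 25%, equivalent to 1 / 0.75 = 1.33 times as many women
- r = 0.7: 1 − 0.49 = 0.51, a fall of 49%

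These reductions do not depend on the SD or the treatment effect.

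**3. Power.** For a standardized difference d (difference divided by SD), two-sided alpha 0.05 and 469 per arm:

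Power = Φ( d × √(469/2) / √(1 − r²) − 1.96 ), with r = 0 for the unadjusted comparison.

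Example: unadjusted power of 70% needs d × √(469/2) = 1.960 + 0.524 = 2.484, so d = 0.162. At r = 0.5 this becomes 2.484 / 0.866 = 2.868, and Φ(2.868 − 1.960) = 81.8%, a gain of 11.8 points.

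Gain in percentage points:

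| Unadjusted power (d) | r = 0.3 | r = 0.5 | r = 0.7 |
|---|---|---|---|
| 60% (0.145) | 4.1 | 12.4 | 27.3 |
| 70% (0.162) | 4.0 | 11.8 | 23.6 |
| 80% (0.183) | 3.6 | 9.9 | 17.5 |
| 90% (0.212) | 2.5 | 6.3 | 9.5 |
| 97% (0.25) | 1.1 | 2.4 | 3.1 |
| 99.6% (0.30) | 0.2 | 0.4 | 0.4 |

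The gain is material for small effects with a moderate or high correlation, and negligible once the effect is large enough to be detected anyway.

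**The case against.** **The protocol does not prescribe an unadjusted test for pain.** A reader might infer that continuous outcomes in general are to be compared by an unadjusted test picked from histograms. The text does not support that. Both sentences close a paragraph about baseline comparability, and weight loss, PIMS and MBFES have a Wilcoxon test fixed in advance. Strictly, the protocol names no test for pain. If that were all, it could be left to a statistical analysis plan, which is not at hand.

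This part stands, but it does not dispose of the point. Sections 6.4.3.2 and 6.4.4 do take a position on adjustment: optional and exploratory. An analysis plan that made a baseline-adjusted model the main pain analysis would have to depart from that.

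**Adjusted analyses are foreseen.** This is correct, and their list of continuous outcomes is given by example, so pain could be included. It would be wrong to say that the protocol rules adjustment out. It simply does not commit to it or name the baseline score.

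**The correlation is unknown.** Concomitant medication is unrestricted (6.1.3), so analgesia begun between the two readings could lower r. Membrane status, one source of differing entry pain, is already a stratification factor. Nothing in the protocol supports any particular r. This stands, and it is why the gain is given as a range.

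**The baseline score follows randomization in an open-label trial.** A woman who knows her arm may score differently, and adjusting for a score that allocation has influenced can bias the arm difference. The unadjusted comparison avoids this. It is the most serious objection. It limits how the adjusted result may be used and makes the sensitivity analysis necessary.

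**Conclusion.** The point holds as a modest improvement. The protocol collects a same-scale baseline for an outcome in its central hypothesis, and no analysis names or commits to it. The generic test wording is unadjusted and reaches pain only by inference; the adjusted route is optional and exploratory.

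The gain rests on an assumed r of 0.3 to 0.7 and on 469 women per arm with both scores. Residual variance falls by 9% to 49%. Power rises by about 4 to 24 points if it would otherwise be about 70%, 4 to 18 at 80%, 2.5 to 10 at 90%, and about 3 points or less for d of 0.25 or more. A reader might take one of these ranges as the power the plan loses. The documents cannot support any single figure, because they give neither r nor a target difference for pain.

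Spontaneous vaginal delivery, its test and its sample size are unaffected.

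**What to change.** Name one main analysis of 2-hour VAS: linear regression on arm, baseline VAS, site and membrane status (the last two being the stratification factors), reporting the adjusted mean difference with a robust 95% confidence interval. Keep the unadjusted comparison as a sensitivity analysis, and state in advance whether it is of means or ranks. Exempt this model from the exploratory label in Sections 6.4.3.2 and 6.4.4.

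Because of the timing of the baseline score:
- for remaining participants, take it before allocation is disclosed where feasible;
- compare baseline VAS between arms as a check;
- write down now that the unadjusted analysis will be relied on if the arms differ. Such a difference could be chance or knowledge of the arm, and the check cannot tell them apart.

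The analysis change is wording only and needs no new data. Moving the baseline score ahead of disclosure is a small procedural change. It cannot help women already enrolled, who may be the majority: this version is dated July 2025 and the last enrollment was expected in June 2026 (Section 5.1.1).

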The primary outcome (spontaneous vaginal delivery) and other categorical secondary outcomes will be compared between trial groups using Chi-square or Fisher's exact tests as appropriate. The estimates of the relative risk and 95% confidence intervals (95% CI) associated with the primary and secondary outcomes will be calculated using Agresti and Coull method. The time to event regression analyses for labor length (regardless of delivery mode) and labor length censored for cesarean will be evaluated by Kaplan-Meier estimates and plots, and tested with the log-rank test, whereas Cox proportional hazards analysis will be used in adjusted analyses accounting for Bishop scores at study entry (proportionality assumption will be checked graphically with $\ln(-\ln\text{Survival})$ plots), and results summarized using hazard ratios (HR) and 95% CI). A sensitivity analysis will be performed using the induction method that the patient actually received (per-protocol analysis) to determine whether crossovers influenced the results. The distribution of maximal percent newborn weight loss is not expected to follow a normal distribution in the population, so we plan to use Wilcoxon Rank Sum Tests to compare the distribution of the maximal percent weight loss between treatment groups, and summarize the results as medians (25th and 75th percentiles) and bootstrapped 95% CIs. Similarly, the distributions of the PIMS survey scores and MBFES survey scores are not expected to follow normal distributions in the population, so we will use Wilcoxon Rank Sum Tests to compare the distribution of the MBFES scores between treatment groups and summarize the results using the group medians (25th and 75th percentiles) and bootstrapped 95% CIs.

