6.4.3.2 Secondary Objectives Analyses

Adjusted Analyses and Planned Subgroup Analyses

We will perform other analyses as needed aimed at obtaining adjusted assessments of treatment effectiveness, adjusting for baseline patient characteristics (covariates). The objectives of these analyses are to estimate the influence of covariates on the outcome and to use covariates to improve the estimated difference between treatment groups. The Poisson regression model (link=log) with robust standard errors stratified by study site will be used to identify and estimate the effect of multiple prognostic factors on the probability of spontaneous vaginal delivery and other categorical outcomes, with results summarized as adjusted risk ratios. For continuous secondary outcomes such as maximal newborn weight loss and PIMS and MBFES survey scores, quantile regression, e.g., modeling 50th percentile, will be considered to adjust for prognostic factors. Interaction tests will be used to determine whether the effectiveness of nipple stimulation therapy significantly differs across these subgroups. These analyses will be considered exploratory in nature and will not be viewed as providing confirmatory tests of hypotheses.

The following pre-specified subgroup analyses will be conducted:

1. Study site
2. Amniotic membrane status (intact versus ruptured) at enrollment
3. Presence versus absence of maternal diabetes (inclusive of pre-gestational and gestational diabetes)
4. Insurance type (commercial versus public insurance)
5. Maternal race (Black versus White versus Other)
6. Obesity (obese versus non-obese)

In separate models, each of these sub-group variables will be included as an additional covariate in the models for outcomes of interest, plus their interaction with treatment variable; followed by stratified analyses (by each of the above variables) of the effect of treatment on each outcome of interest.

Data Analysis Plan for the Biospecimen Sub-Study:

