6.4.3.6 Health economic evaluation

To estimate difference in cost and difference in quality adjusted life years (QALY) between the intervention and comparator groups, we will use a generalized linear model (GLM) with log link and gamma distribution for cost (given skewness in cost data) and identity link and normal distribution for QALY. Explanatory variable will be an indicator for intervention (vs. comparator) group. All analyses will follow the intention to treat principle. As randomization will be stratified by study site and amniotic membrane status, we will test if they are associated with cost or QALY and decide whether to include them as covariates in analysis. Cost-effectiveness will be evaluated by calculating the incremental cost effectiveness ratio (ICER), defined as $\Delta C/\Delta E$ where ΔC denotes the estimated difference in cost between the intervention and comparator groups and ΔE reflects the estimated difference in QALY between the two groups. ICER informs the additional cost associated with the intervention for each additional QALY gained. We will use non-parametric bootstrap resampling to estimate 95% CI of ICER and produce a cost-effectiveness plane and cost-effectiveness acceptability curve. In special situations where the intervention leads to significantly lower cost and higher QALY, the intervention is considered the dominant strategy. In situations where there is no significant difference in QALY between the two groups, a comparison of cost will inform the cost-effectiveness of the intervention; and vice versa. Our primary cost-effectiveness analysis will examine costs and health effects up to 2 weeks postpartum. We will also conduct two secondary analyses by: 1) extending the time period to 6 months postpartum, and 2) calculating QALY using participants' EuroQol five dimensions (EQ-5D) visual analogue scale (VAS) rating as a utility score (with linear transformation to a 0 to 1 scale).

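### Agresti-Coull, a one-proportion interval, is named for the relative risks, and the primary test and estimate use neither randomisation factor; both should be fixed, at almost no cost

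*Protocol*

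**What the plan says.** Section 6.4.3.1 of the protocol fixes the primary analysis in two consecutive sentences. Spontaneous vaginal delivery and the categorical secondary outcomes "will be compared between trial groups using Chi-square or Fisher's exact tests as appropriate". The relative risks and 95% CIs "associated with the primary and secondary outcomes will be calculated using Agresti and Coull method". No other method is given for these intervals, and no interval is named for the risk difference.

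Randomisation (section 6.1.2) is "stratified by study site and amniotic membrane status (intact versus ruptured"). With three sites this makes six strata. Later sections treat the two factors in different ways:

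- **Adjusted analyses (6.4.3.2, repeated in 6.4.4):** "The Poisson regression model (link=log) with robust standard errors stratified by study site will be used" for the categorical outcomes. Membrane status is not named in that sentence. It is a listed subgroup variable, and each subgroup variable enters its own separate model with a treatment interaction. The section labels these analyses exploratory.
- **Cost and QALY models (6.4.3.6):** for the same two factors, "we will test if they are associated with cost or QALY and decide whether to include them as covariates in analysis".

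The trial is sized on the absolute scale (section 6.4.2): "estimated 74% versus 64%) in spontaneous vaginal delivery with 90% power (alpha of 0.05").

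**The concern.** Agresti-Coull adds about two successes and two failures to one arm's count and forms a Wald interval around the shifted proportion. It takes a single sample as input. An analyst told to obtain a relative-risk interval from it has to invent a second step, and different second steps give different answers. If the sentence is read as covering only the arm-level proportions, the relative risk is left with no interval method at all. The protocol names a method here and the method does not fit, so this is not detail left to a SAP.

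The sentence also governs the secondary outcomes. Section 6.4.3.3 uses the maternal and perinatal morbidity comparisons to look for safety signals, and several of those events (death, intensive care admission, very low Apgar score) are likely to be few. The improvised versions diverge most at low counts.

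The second matter is stratification. When randomisation is stratified on factors that predict the outcome, an unstratified test uses a standard error that is slightly too large. The size of the effect depends on how strongly the strata predict delivery mode.

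**Working it through.** **Inputs.** 64% versus 74%, 90% power, alpha 0.05 and 494 per arm (6.4.2); "All sample size and power estimates are based on two-tailed tests"; the sample is set "to detect a 10% absolute increase while accounting for an expected 5% attrition rate"; 1:1 allocation and six strata (6.1.2). After 5% attrition, 494 × 0.95 ≈ 469 per arm. At the design rates this is about 347/469 versus 300/469.

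**The plan's own figure.** The two-proportion formula with pooled null variance gives 447.4 per arm. The continuity correction raises this to 467.2, rounded up to 468. Then 2 × 468 / 0.95 = 985.3, so 986 against the stated 988. The same formula comes within 2 of all seven rows of the sample size table. The sizing therefore corresponds to an unstratified, continuity-corrected two-proportion test.

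**What Agresti-Coull yields.** With z² = 3.84, p̃ = (x + 1.92)/(n + 3.84) and the limits are p̃ ± 1.96·√[p̃(1 − p̃)/(n + 3.84)].

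- 347/469: 0.698 to 0.778
- 300/469: 0.595 to 0.682

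These are two separate intervals. Neither is an interval for the ratio.

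**Two-sample interval for the primary outcome.** RR = 347/300 = 1.157. SE(log RR) = √(1/347 − 1/469 + 1/300 − 1/469) = 0.0442. The interval is exp(0.1455 ± 1.96 × 0.0442) = 1.061 to 1.261. Ways of completing the named method compare as follows:

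| Reading | 95% interval for RR |
|---|---|
| Plain log-RR | 1.061 to 1.261 |
| Agresti-Coull arm limits combined on the log scale (MOVER) | 1.061 to 1.262 |
| Log-RR on Agresti-Coull-shrunk proportions | 1.060 to 1.260 |
| Opposite Agresti-Coull limits divided | 1.024 to 1.306 |

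The first three agree to about 0.002. The fourth is about 40% wider (0.282 against 0.200).

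**Risk difference at the same counts.** 0.740 − 0.640 = 0.100; SE = √(0.740 × 0.260/469 + 0.640 × 0.360/469) = 0.030; 95% interval about 0.041 to 0.159. This is the scale on which the trial was sized.

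**Rare outcome.** The counts of 5 versus 1 per 469 are an illustration and do not come from the protocol. Crude RR = 5.0. With shrunk proportions, RR = (5 + 1.92)/(1 + 1.92) = 2.4. For 1/469, p̃ = 2.92/472.84 = 0.0062 with half-width 0.0071, so the lower limit is −0.0009. A negative limit cannot be used in a ratio.

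**Stratification.** The protocol gives no stratum-specific rates, so these are assumptions: 30% with ruptured membranes, three equal sites with control rates spread around 64%, a membrane-status gap, and a 10-point effect. Simulation used 469 per arm and 40,000 runs per row, comparing the unstratified chi-square with Cochran-Mantel-Haenszel (CMH) over six strata.

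| Site spread / membrane gap (points) | Power, chi-square | Power, CMH | SE ratio, CMH to chi-square | Type I, chi-square | Type I, CMH |
|---|---|---|---|---|---|
| 0 / 0 | 91.3% | 91.3% | 1.001 | 5.0% | 5.0% |
| ±5 / 5 | 91.5% | 91.6% | 0.995 | 5.0% | 5.1% |
| ±5 / 10 | 91.5% | 91.8% | 0.992 | 4.8% | 4.9% |
| ±10 / 10 | 91.7% | 92.3% | 0.980 | 4.8% | 5.1% |
| ±10 / 15 | 92.0% | 92.8% | 0.974 | 4.5% | 5.0% |

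A second simulation used six equal strata with control rates from 48% to 80%. It gave type I error 4.4% for the unstratified test, and power 91.8% against 92.5% stratified. An extreme spread of 42% to 88% gave 4.0%, and 92.9% against 94.1%.

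**The case against.** The best defence is that the trial's decision rests on the chi-square or Fisher test, which is fully defined and matches the sample size calculation. Three sensible ways of completing the interval agree to about 0.002, so the misnamed method cannot change the primary conclusion. That stands.

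A reader might go further and infer that the reported interval would be badly distorted. Dividing opposite Agresti-Coull limits has about 99.5% null coverage and excludes 1 in only about 71% of trials at the design effect, against about 91% for the log-RR interval. But the protocol nowhere proposes that procedure, and the 71% is not the power of the planned test.

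A reader might also infer that precision is certainly lost, or that membrane status is ignored altogether. Neither is supported. The loss depends on stratum rates that the protocol does not report. Every scenario keeps more than 90% power, and the unstratified test is at or slightly below its nominal level. Membrane status does enter the planned subgroup models, although these are exploratory. An unadjusted primary comparison is defensible in a pragmatic trial.

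A risk difference with its interval could also be added in a SAP, and section 6.4.3.1 does not exclude one. That weakens its omission as a criticism, but it remains worth stating, because the design effect is absolute.

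What the defence does not answer is that a method is named which does not define the interval, and that the same sentence covers rare safety outcomes, where the choice of completion matters.

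**Conclusion.** The point holds as something that should be fixed; it does not threaten the trial's conclusion. The named interval method is wrong for a relative risk. At the design rates the practical effect on the primary outcome is negligible provided a proper two-sample interval is used (about 1.06 to 1.26), and the p-value is untouched. The larger exposure is in rare safety outcomes. The 5 versus 1 example, with its fall from 5.0 to 2.4 and its negative single-arm limit, depends on chosen counts and on one improvised use of the method.

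Leaving both randomisation factors out of the primary test and estimate costs roughly 0 to 1 point of power and brings the type I error to about 4.4% to 5% over the moderate assumed stratum rates. Only the extreme 42% to 88% spread goes slightly beyond this. If the strata are not prognostic, nothing is lost. The pre-test of the strata in the cost and QALY models is a minor inconsistency in a secondary evaluation and adds no weight to the primary point.

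**What to change.** 1. In section 6.4.3.1, delete the reference to Agresti and Coull.
2. State that the primary relative risk and the risk difference will be reported with two-sample 95% CIs. Take them from a Mantel-Haenszel analysis over the six strata, or from the protocol's own robust Poisson model with site and membrane status as covariates. In the second case, name a companion method for the risk difference, since a log link does not give one directly.
3. Make the primary test the matching Cochran-Mantel-Haenszel test.
4. For rare outcomes, name a two-sample score interval for the relative risk.
5. For consistency, add membrane status beside site in the adjusted Poisson model (6.4.3.2 and 6.4.4), and include both factors in the cost and QALY models (6.4.3.6) without pre-testing.

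The cost is a few sentences in the protocol, or in the SAP if there is one. No new data are needed, because both factors are recorded at randomisation, and the sample size of 988 is unchanged. The change should be made before outcomes are compared by arm, so that the interval method cannot be chosen after the results are known.
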